#### **2.4.4.2 Compliance**

Compliance to the treatment regimen will be monitored in terms of the percentage of scheduled infusions the patient receives during the treatment periods, irrespective of whether the infusion was total or partial. This is calculated as:

$100 \times (\text{number of infusions received}) / (\text{number of infusions intended to be received})$

For PAP, the number of infusions intended to be received is 27 over 52 weeks for a patient who complete PAP.

Noncompliance in PAP is defined as missing 2 or more consecutive infusions in PAP (excluding for cause misses, such as when the missed doses are required by the protocol due to a DLT) or 4 or more infusions in total in the 52-week PAP treatment period.

Noncompliance in PAP+ETP is defined as missing 4 or more infusions in every 52-week period following PAP treatment period until the end of study.

Treatment compliance for overall PAP will be summarized descriptively as quantitative variable using mITT population and randomized treatment group.

The percentage of patients whose compliance is  $\leq 85\%$  (missing 4 or more infusions out of scheduled 27 infusions in PAP) will be provided. In addition, number and percentage of patients with noncompliance, and by reasons (missed 2 or more consecutive infusions not for cause (“not for cause” means there is no justifiable reasons for a missed dose, eg., DLT), or missed 4 or more infusions in total in the 52-week PAP) will be provided.

Similar summaries will be provided for PAP+ETP.

A case of overdose will be reported as an AE and will be summarized with AE. An overdose is defined in Section 10.4.1.3 of the protocol.

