8.1.1 Treatments administered

The term “study drug” will refer to olipudase alfa and placebo (saline [0.9% sodium chloride solution]), but only olipudase alfa is an IMP.

During clinical development of olipudase alfa, incremental changes were made to the olipudase alfa manufacturing process. The different processes are referred to as Process B, C(■) and C(■).

Dosing with study drug will be by intravenous infusion every 2 weeks (± 3 days) in reference to the date of the first infusion (Day 1) for each patient. The 52-week treatment period of the PAP will begin on Day 1 with the first infusion of study drug.

To maintain the double-blind, all patients regardless of treatment assignment will undergo dose escalation under the same conditions and according to the schedule provided in [Table 1](#).

All infusions will take place in a monitored setting with ready access to emergency resuscitation equipment and medications (see [Section 10.1](#) for information on timing for in-patient hospitalization). One rechallenge each will be allowed for doses administered at Week 0 (0.1 mg/kg olipudase alfa or placebo) and at Week 4 (0.3 mg/kg olipudase alfa or placebo). Patients who are unable to tolerate the rechallenge at those doses will be discontinued from the study. If a patient is discontinued due to inability to tolerate rechallenge, (ie, a second dose of 0.3 mg/kg olipudase alfa), then an additional patient may be randomized but only during the PAP. During the PAP and ETP, in-patient hospitalization will be required preinfusion and for at least 24 hours after the infusion during dose escalation (ie, through Week 16 and Week 70, respectively) and may be required at the quarterly and yearly visits up through the end of Year 2; in-patient hospitalization may be necessary during quarterly and yearly study visits in Years 3 through 5.

Home infusion may be initiated during COVID-19 (ETP) by trained home nurses every 2 weeks (± 3 days), if agreed between the investigator and the sponsor, in compliance with applicable country-specific regulations. Patients must meet specific eligibility requirements ([Section 10.1.1](#)). Patients who initiated home infusion during the COVID-19 pandemic, and continue to be on home infusion, may continue receiving home infusion by trained home nurses in the ETP every 2 weeks (± 3 days) until the end of the ETP (refer to [Appendix B](#) for Germany).

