8.7.1 Treatment accountability and compliance

Compliance to the treatment regimen will be monitored in terms of the percentage of scheduled infusions the patient receives through the treatment periods. Every effort should be made to ensure that no infusion is missed.

Noncompliance is defined as missing 4 total infusions (not for cause, such as when the missed doses are required by the protocol due to a DLT) per each 12-month period. As they are identified, the investigator should discuss noncompliant patients on a case by case basis with the sponsor's medical monitor (or designee).

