## 2.2.2 Protocol deviations

Protocol deviations are qualitative and quantitative in nature. Qualitative deviations are evaluated and reported in a list by study monitoring team and reviewed by the study team. Quantitative deviations are programmed in SAS from the data, and reviewed by the study team. In both cases, the study team determines whether a deviation is minor, major or critical before the unblinding in PAP (and any that occurs in ETP at the end of study before the database lock). A summary table and a data listing of major or critical deviations will be provided, including, but not limited to, prohibited medication use as well as non-compliance.

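### The SAP's compliance cut of ≤85% does not select a PAP completer who misses exactly 4 of 27 infusions, and its 4-missed noncompliance rule lacks the protocol's for-cause exemption

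*SAP*

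**What the plan says.** SAP 2.4.4.2 measures compliance "in terms of the percentage of scheduled infusions the patient receives during the treatment periods", as 100 × infusions received / infusions intended, with partial infusions counted as received. It fixes the denominator for completers: "For PAP, the number of infusions intended to be received is 27 over 52 weeks for a patient who complete PAP". One planned summary begins "The percentage of patients whose compliance is" and sets the cut at ≤85%, with the gloss "missing 4 or more infusions out of scheduled 27 infusions in PAP".

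The same section defines PAP noncompliance by two limbs. The first is two or more consecutive misses, with for-cause misses such as DLT holds left out. The second is four or more misses in total, with no such exclusion. The by-reason summary repeats this placement. The PAP+ETP rule, four or more misses in each later 52-week period, also has no exclusion.

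Protocol 8.7.1 has a single rule, a total of 4 per 12-month period, and the exemption sits on it: "missing 4 total infusions (not for cause, such as when the missed doses are required by the protocol due to a DLT) per each". SAP 2.2.2 names noncompliance among the items in its summary and listing of major or critical deviations: "including, but not limited to, prohibited medication use as well as non-compliance".

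**The concern.** The SAP presents a percentage and a count as the same category. If they differ, the reported number depends on which one the programmer implements. The same section also asks for the number of patients with four or more misses in total, so a completer with exactly 4 would appear in that row and be absent from the ≤85% row, with nothing in the text to explain it.

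The exemption is a second, independent problem of consistency between documents. Protocol 8.1.4 requires dosing to stop temporarily for a potential DLT pending DMC review, and Protocol 8.1.3.2 treats an infusion delayed by more than 3 days as missed. Holds made under the protocol can therefore generate misses. Under one document these do not count towards noncompliance; under the other they do.

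**Working it through.** **1. The denominator.** Protocol 8.1.1: "Dosing with study drug will be by intravenous infusion every 2 weeks". From Week 0 to Week 52 inclusive that is 52/2 + 1 = 27 infusions. The SAP's 27 is reproduced.

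**2. The percentage against the count**, for a PAP completer, compliance = 100 × (27 − missed)/27:

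| Missed | Received | Compliance | ≤85%? | 4 or more missed? |
|---|---|---|---|---|
| 3 | 24 | 88.89% | no | no |
| 4 | 23 | 85.19% | **no** | **yes** |
| 5 | 22 | 81.48% | yes | yes |
| 6 | 21 | 77.78% | yes | yes |

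Equivalently, 0.85 × 27 = 22.95, so the most infusions a completer can receive and still be at or below 85% is 22. The stated equivalence is not reproduced; the definitions part at exactly 4 misses and nowhere else among completers.

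**3. Rounding.** To one decimal, 23/27 is 85.2% and still fails the cut. To a whole percent it is 85% and passes. The SAP's rule on rounding to the precision of a criterion (general common rules under 2.4.6) is written for PCSA values only; no rule covers compliance.

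**4. Other denominators.** The SAP gives 27 only for completers. Assuming that fewer infusions are intended for an early discontinuer:
- 4 missed of 26 gives 22/26 = 84.62%, which the cut does catch.
- 1 missed of 6 gives 5/6 = 83.33%, which is also caught, after a single miss.
- 6/7, 12/14 and 18/21 are all 85.71%, with 1, 2 and 3 misses; these are not caught by ≤85% but would be caught by <86%.

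**5. The exemption, side by side.** Take a patient with 4 misses in one year, all required by a DLT:

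| Rule | Misses that count | Result |
|---|---|---|
| Protocol 8.7.1, 4 in total, for-cause exempt | 0 | not noncompliant |
| SAP, 2 or more consecutive, for-cause exempt | 0 | not met |
| SAP, 4 or more in total in PAP, no exemption stated | 4 | noncompliant |
| SAP, PAP+ETP, no exemption stated | 4 | noncompliant (if in a later 52-week period) |

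The protocol's parenthesis is awkwardly worded, but exempting for-cause misses is its only sensible reading. Version drift does not explain the difference: the SAP is built on Amended Protocol 11, and the change summaries for Amended Protocols 12 to 15 list no change to Section 8.7.1.

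**The case against.** The best defence of the cut is that the SAP prints the intended category in words beside the percentage, and 23/27 is 85% at the precision in which the cut is written. A careful programmer may follow the count, and then nothing goes wrong. That stands as far as it goes: this is an instruction with two readings, not a certain miscount. But the SAP does not say which reading governs.

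A reader might infer that every patient who misses exactly 4 infusions is misclassified. The documents do not support that. The 27 applies to completers only, and with a smaller denominator 4 misses fall below 85%. Nor should the ≤85% table and the noncompliance table be expected to agree in general, because the latter has the added 2-consecutive limb.

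A reader might also infer that DLT holds will remove olipudase patients from the per-protocol analysis. No text makes SAP noncompliance an exclusion. Under SAP 2.2.2 the study team grades each deviation before PAP unblinding, and under SAP 2.3.1.2 only critical or major deviations expected to interfere with the primary endpoints exclude a patient. The documents give no rate of DLT holds by arm.

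Finally, SAP 1.5 does not mention the different rule, but its heading limits it to the protocol's statistical section, and Section 8.7.1 is about treatment accountability. The inconsistency is real; calling it an omission from SAP 1.5 goes further than that section's scope clearly allows.

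**Conclusion.** Both parts hold in a narrow form. Followed literally, with unrounded compliance, the ≤85% row omits PAP completers who miss exactly 4 infusions, although the SAP's own words include them. And a patient whose misses were required by the protocol can be noncompliant in the SAP tables while not noncompliant under Protocol 8.7.1.

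The size is small. With 36 patients randomized 1:1, each affected patient moves a reported percentage by 1/18 = 5.6 points in one arm. How many would be affected is unknown, since the documents do not project missed infusions. The consequences are confined to descriptive compliance and deviation summaries. The primary analysis in the mITT population does not use compliance. The per-protocol run is one sensitivity analysis (SAP 2.4.5.1), and an effect on it would need two further judgements made before unblinding.

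This rests on two assumptions: that compliance is not rounded to a whole percent, and that the for-cause wording in SAP 2.4.4.2 applies only to the limb it is attached to, as the by-reason summary confirms.

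**What to change.** In SAP 2.4.4.2:

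1. Replace the ≤85% category by the count it is meant to represent: 4 or more scheduled infusions missed. State how scheduled infusions are counted for patients who leave the PAP early. Do not move the cut to <86%: it works for completers but would flag early discontinuers with only 1 to 3 misses, as the 85.71% cases show.
2. Reconcile the 4-total limb, and the PAP+ETP rule, with Protocol 8.7.1. Either apply the not-for-cause exemption there too, or state openly that the SAP departs from the protocol definition and why. If both counts are of interest, report misses for cause and not for cause separately.

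The cost is a few lines of text and a small programming change. No data collection, primary analysis or sample size is affected.

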## **2.4.5 Analyses of efficacy endpoints**

Efficacy data will be analyzed by randomized treatment group in mITT population at scheduled time point. The statistical analyses will compare olipudase alfa versus placebo within PAP; the difference between two treatment groups is calculated as olipudase alfa minus placebo.

Primary analyses period is 52 weeks.

Efficacy analyses will use mITT population unless specified otherwise. This will include patients who used rescue therapy, but their data after rescue will NOT be included in the analysis. Sensitivity analyses including data beyond rescue therapy may be undertaken if appropriate.

Baseline values are generally the latest value before the first infusion of the study drug, except for platelets and hemoglobin which are part of hematology parameters; for hematology parameter baseline definition, please refer to [Section 2.6.1](#).

### **2.4.5.1 Analysis of primary efficacy endpoint(s)**

The percentage change in DLco (% predicted) from baseline to 52 weeks will be analyzed in the mITT population using a mixed model for repeated measures (MMRM) (17, 18). The MMRM will include baseline DLco, baseline age, treatment arm, study visit, and study visit by treatment arm interaction as covariates; have an unstructured variance-covariance matrix; and be fit using restricted maximum likelihood estimation. If this model fails to converge, the following variance-covariance structures will be tested in this order: Toeplitz (equal variances and a separate correlation for each level of separation between the time points), AR(1) (first-order autoregressive, equal variances and exponentially decreasing correlations), CS (compound symmetry, equal variances and equal pairwise correlations across fixed time points). The first (co)variance structure yielding convergence will be used as the primary analysis. Comparisons between treatment arms will be made using least-square mean contrasts at the 52 week visit with denominator degrees of freedom estimated using the Kenward-Roger approximation (19). When a variance-covariance structure other than unstructured is used, then the denominator degrees of freedom will be estimated using the between within method (DDFM=BW in SAS PROC Mixed).

Example SAS code for the MMRM is:

```
ods output Diffs = out1
      LSMeans = out2;
proc mixed data = DATAIN method = reml;
  class TRTPN WEEK USUBJID;
  model PCHG_DLCO = BL_DLCO BL_AGE TRTPN|WEEK / s ddfm=kr;
  repeated WEEK / type = un subject = USUBJID r;
  lsmeans TRTPN TRTPN*WEEK / cl diff;
run;
```

where TRTPN = treatment group, WEEK = (Week 26, Week 52), USUBJID = unique patient ID, PCHG\_DLCO is the percent change from baseline in DLco (%predicted), BL\_DLCO is the baseline DLco (% predicted) value, BL\_AGE is the baseline age,

type =

UN = unstructured covariance

TOEP = Toeplitz covariance

AR(1) = first-order autoregressive covariance

CS = compound symmetry covariance

The MMRM assumes data missing-at-random (MAR) and will include all DLco observations except for measurements made after the initiation of rescue therapy. In addition, for patients who do not have Week 52 value available but have a PFT value measured after Week 38 infusion (eg, patients discontinuing the study or initiating rescue therapy after Week 38 but before Week 52 may have the PFT measurements available from early discontinuation visit or right before rescue therapy starts), these values will be used as Week 52 value for analysis purposes; Week 52 DLco will not be considered missing in such situations. This idea is based on the clinical concept that PFT measurements are similar within a 12-week period.

The percentage change in spleen volume (MN) and the change in the splenomegaly-related score (for US, SRS is part of primary endpoints) will be analyzed using an analogous MMRM model.

The summary plots of the LS means from the MMRM of the percentage change in DLco (% predicted), the percentage change in spleen volume (MN) and the change in the splenomegaly-related score from baseline up to Week 52 with 95% CIs will be provided.

Sensitivity analyses for the primary efficacy endpoints to support robustness of results will include the following:

1. The MMRM described above will be run using the per-protocol population. This analysis will demonstrate whether the results vary depending on the population analyzed.
2. The MMRM described above will exclude observations made after the initiation of rescue therapy. As a sensitivity analysis, the observations collected after the initiation of rescue therapy will be included in the MMRM; the treatment arm for rescued patients will remain

as randomized treatment.

The MMRM planned for the primary efficacy analysis assumes MAR. To assess the robustness of the primary results to that assumption a pattern mixture model will be used (see [Section 2.6.6](#) for details).

3. The MMRM planned for the primary efficacy analysis assumes multivariate normality. To assess the robustness of conclusions under this assumption, nonparametric testing method will be used: A Wilcoxon-Mann-Whitney (WMW) will be used to compare the primary efficacy endpoints; missing Week 52 data will be imputed using LOCF, excluding patients who initiate rescue therapy.

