11.5.2.1 Primary efficacy analysis

The 2 primary efficacy endpoints (percentage change in spleen volume in MN from baseline to Week 52 [combined with change in SRS from baseline to Week 52 in the US only, and is referred to as the “combination spleen endpoint”]) and percentage change in DL_{CO} in percent predicted from baseline to 52 weeks) will be analyzed in the mITT population using the mixed model for repeated measures.

For percent change in DL_{CO} (% predicted) from baseline, the mixed model for repeated measures (MMRM) will include baseline DL_{CO} (% predicted), baseline age, treatment arm, study visit (Week 26, Week 52), and study visit by treatment arm interaction as covariates; have an unstructured variance-covariance matrix; and be fit using restricted maximum likelihood estimation. Comparisons between treatment arms will be made using least-square mean contrasts at the 52 week visit.

The analysis will include all DL_{CO} observations after baseline in the first 12 months of the study regardless of the treatment discontinuation status, with the exception that measurements made after the switch of treatment (eg, placebo patients switch to olipudase alfa after meeting the rescue criteria) will not be considered. For the primary analysis, missing data will not be imputed and will be assumed as Missing at Random (MAR).

Similar analyses will be performed for the spleen volume (MN) and the splenomegaly-related symptom score (SRS), when baseline value of the spleen volume (or SRS) will be used as covariate.

Descriptive assessment of MAR assumption and sensitivity analyses to assess the impact of missing data are described in the SAP.

Hypothesis tests will be 2-sided and adjusted for multiple comparisons to maintain a family-wise Type 1 error rate of 5%. The details of multiplicity adjustments are provided in [Section 11.5.4](#).

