#### **2.4.5.4 Subgroup analyses for the primary endpoints in PAP**

The consistency of the treatment effect in PAP will be evaluated as follows for percentage change from baseline to Week 52 of spleen volume (MN) and percentage change from baseline to Week 52 of % predicted DLco separately:

- Spleen volume by baseline spleen volume severity (severe vs not severe). Severity is defined as baseline spleen volume >15 multiple of normal (MN).
- % predicted DLco by baseline % predicted DLco severity (severe vs not severe). Severity is defined as baseline % predicted DLco <40%.

In addition, for the endpoints of percentage change from baseline to Week 52 of spleen volume (MN), SRS, and % predicted DLco, the consistency of treatment effect in PAP will be assessed by the following subgroups:

- Baseline ALT or AST abnormality (ALT or AST  $\geq$ 1 ULN vs ALT and AST <1 ULN)
- Baseline total bilirubin abnormality (total bilirubin  $\geq$ 1.5 ULN vs total bilirubin <1.5 ULN)

For the percentage change from baseline to Week 52 of spleen volume (MN), whether or not the presence of portal hypertension has an effect on olipudase alfa treatment will be assessed by the following subgroup:

- Presence vs absence of portal hypertension at baseline (detected signs of portal vein hyperpressure is “likely severe portal hypertension” or “likely portal hypertension” for presence of portal hypertension vs detected signs of portal vein hyperpressure is “unlikely portal hypertension” for absence of portal hypertension)

Descriptive summaries on the observed values, change from baseline and percent change from baseline to Week 52 of spleen volume (MN) for patients with severe portal hypertension at baseline will be provided as well if there are at least 3 patients identified with severe portal hypertension at baseline. If the number of patients with severe portal hypertension at baseline is low (<3), only individual patient data will be provided in listings.

Due to the small sample size in these subpopulations, treatment difference within the subgroup will be difficult to interpret. Therefore, the focus of these analyses will be on assessment of interaction between subgroups and the treatment.

For each subgroup, same MMRM models for the primary efficacy endpoints using data from the specific subgroup only will be conducted to provide estimate of treatment effect within each

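### The MMRM fallback list gives DLco and spleen volume one alternative rather than three, and every listed fallback assumes equal variance across visits, so the Week 52 standard error is biased if variance changes over time

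*SAP*

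**What the plan says.** SAP 2.4.5.1 specifies the primary model for DLco: it must "have an unstructured variance-covariance matrix; and be fit using restricted maximum likelihood estimation", with Kenward-Roger degrees of freedom for the Week 52 contrast. Protocol 11.5.2.1 names only the unstructured matrix and gives the visits: "treatment arm, study visit (Week 26, Week 52), and study visit by treatment arm interaction as covariates".

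The SAP then adds a fallback rule: "If this model fails to converge, the following variance-covariance structures will be tested in this order: Toeplitz (equal variances", followed by "AR(1) (first-order autoregressive, equal variances and exponentially decreasing correlations" and "CS (compound symmetry, equal variances and equal pairwise correlations across fixed time points". Whichever converges first is the primary analysis. Under any fallback, "the denominator degrees of freedom will be estimated using the between within method (DDFM=BW in SAS PROC Mixed".

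Spleen volume and SRS use an analogous model. Abdominal MRI is done at Weeks 26 and 52 in the primary analysis period (Protocol 1.2.1.2). SRS is collected at Weeks 14, 26, 38 and 52 (SAP 2.6.6), and the platelet model uses the quarterly visits (SAP 2.4.5.2). In SAP 2.4.5.4 the model is also refitted on subsets: "For each subgroup, same MMRM models for the primary efficacy endpoints using data from the specific subgroup only will be conducted".

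**The concern.** A fallback list should offer distinct alternatives, and each should still give a valid standard error for the comparison that carries the claim. Here that comparison is at Week 52 only.

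Two features look wrong. With two visits the three named structures cannot differ as statistical models. And the SAP's own descriptions give all three equal variances, so under a fallback the Week 52 standard error is estimated partly from the spread at earlier visits. If the spread at Week 52 differs from the average over visits, that standard error is wrong, and so are the confidence interval and p-value that would count as primary. The same holds for the SRS component of the US combination spleen endpoint and for the secondary endpoints that borrow the model.

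**Working it through.** **Inputs from SAP 1.3.** 36 randomized 1:1; 11% without a Week 52 result, leaving 36 × 0.89 ≈ 32, or 16 per arm; one common SD per endpoint: DLco 20%, spleen volume 11.8%, SRS 9.4. Neither document gives an SD by visit or a between-visit correlation; both are assumptions below.

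**The plan's own figures.** A two-sample t-test with 16 per arm (noncentral t) gives power 0.928 for DLco (stated 0.93), above 0.999 for spleen volume (stated 0.99) and 0.823 for SRS at 0.15 (stated 0.82). The inputs are read correctly.

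**1. Are the three fallbacks distinct?** An unstructured matrix over T visits has T(T+1)/2 parameters: 3 for T = 2, 10 for T = 4. With T = 2, Toeplitz, AR(1) and CS each reduce to one variance and one correlation. Fitting the SAP's model to simulated data confirms this:

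| Visits | Structure | −2 REML log-likelihood | Week 52 SE |
|---|---|---|---|
| 2 | Toeplitz, AR(1), CS (identical) | 421.785 | 5.748 |
| 2 | Unstructured | 407.194 | 7.314 |
| 4 | Toeplitz / AR(1) / CS | 594.93 / 595.61 / 611.99 | 2.32 / 2.32 / 2.34 |
| 4 | Unstructured | 581.39 | 2.19 |

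So the list holds one alternative for DLco and spleen volume, and three for four-visit endpoints. In the four-visit dataset the true SD rose over time, yet the fallback SEs exceeded the unstructured one: the bias is an average, not a certainty in any one dataset.

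**2. Size and direction of the SE bias.** With complete data, CS estimates the variance at each visit by the mean over visits, so

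SE(fallback) / true SE = √(mean of SD² over visits) / SD at Week 52.

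- SD 8.3, 11.8: √((68.89 + 139.24)/2) / 11.8 = 10.20/11.8 = 0.86.
- SD 10, 11.8: √(119.62)/11.8 = 0.93.
- SD 5.6, 7.5, 8.7, 9.4: √(251.66/4)/9.4 = 7.93/9.4 = 0.84.
- SD 7, 8, 9, 9.4: √(282.36/4)/9.4 = 8.40/9.4 = 0.89.
- Reversed, 11.8, 8.3: 10.20/8.3 = 1.23. Reversed, 9.4, 8.7, 7.5, 5.6: 7.93/5.6 = 1.42.

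**3. Rejection rates under no effect.** CS with between-within df, 16 per arm, complete data, no covariates, adjacent-visit correlation 0.7, 20,000 replicates:

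| Assumed SDs | Nominal 5% | Nominal 15% |
|---|---|---|
| 8.3, 11.8 | 8.4% | – |
| 10, 11.8 | 6.2% | – |
| 5.6, 7.5, 8.7, 9.4 | 9.7% | 22.5% |
| 7, 8, 9, 9.4 | 8.0% | 19.9% |
| Equal | about 5% | about 15% |
| Falling (the two reversed sequences above) | 0.7% to 1.7% | – |

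The unstructured model stayed close to nominal in these runs.

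A smaller simulation with baseline and age in the model and 4 of 36 missing Week 52 (two visits, correlation 0.5, 1,000 runs, error about 1.4 to 2 points) varied r, the ratio of Week 52 SD to Week 26 SD. The 5% test rejected 1.3% at r = 0.67, 3.1% at 0.8, 4.2% at 1, 7.5% at 1.25, 10.9% at 1.5 and 13.4% at 2.

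**4. Degrees of freedom.** Between-within df = nT − 2T − (n − 2). For n = 32 this is 64 − 4 − 30 = 30 with two visits and 128 − 8 − 30 = 90 with four. The two-visit value matches the 30 df of a single-visit comparison. With four visits and the steeper rising SDs, 90 rather than 30 df moved rejection from 9.1% to 9.9%.

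**The case against.** The strongest objection is that the trigger is remote. The rule applies only if the unstructured model fails, and with two visits that model has three covariance parameters. It fitted in every two-visit run made for this check. Even with four visits it converged in all 60 trial fits with 36 patients and all 60 with 12, though not in SAS. This stands, and it sets the severity.

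The direction is also open. A reader might infer that Week 52 p-values under the fallback are too favourable because response diverges during escalation. The documents do not support that. They report no SD by visit; both DLco and spleen visits fall after escalation ends at Week 16; and under no effect, varied drug response adds no variance. Only Week 14, used for SRS and platelets, falls within escalation.

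A reader might call the list empty. It is not: one distinct fallback remains for the primaries and three for four-visit endpoints. Nor is the change to between-within df an important source of error. It has no effect with two visits, and pooling variances would itself raise Kenward-Roger df, to roughly 40 with two visits and 49 with four.

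The primary endpoints have some cover: SAP 2.4.5.1 and 2.6.6 plan a Wilcoxon-Mann-Whitney test and a multiply imputed ANCOVA, neither of which pools variance over visits. For subgroups, SAP 2.4.5.4 says within-subgroup differences will be hard to interpret and puts the focus on interaction. Lastly, BFI item 3, BPI item 3 and FACIT-Dyspnea cite the spleen-volume model without listing visits, so the four-visit count is firm only for SRS and platelets.

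**Conclusion.** The point holds in a limited form. That the second and third steps are redundant for DLco and spleen volume is a mathematical fact. That every listed fallback imposes equal variance is in the SAP's own text. The effect on Week 52 inference is conditional twice over: the unstructured model must fail, and variance must change over visits. When both hold, the 5% test rejects about 6–8% with two visits or 8–10% with four under the rising SDs in the 20,000-replicate runs, more with a steeper rise or missing Week 52 data, and about 1–2% under their mirror images. The 0.15 SRS test rejects about 20–23% under the rising patterns. With constant variance nothing is lost. All these rates rest on assumed visit SDs and correlations.

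Failure is unlikely for DLco and spleen volume. It is somewhat more plausible for SRS and platelets, which need 10 covariance parameters from about 36 patients, and in small subgroups. Severity is low. It is still worth correcting, because the rule would decide a confirmatory p-value and the correction has no effect if the unstructured model converges.

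**What to change.** **Four-visit endpoints.** Put heterogeneous-variance structures (TOEPH, ARH(1), CSH) ahead of any equal-variance structure, and keep Kenward-Roger df. List the visits that enter each model.

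**Two-visit endpoints.** Heterogeneous versions have two variances and one correlation, which is the unstructured model again, so they add nothing. Replace the three-step list with one fallback that does not pool variance over visits, such as ANCOVA at Week 52 with baseline and age. SAP 2.6.6 already fits that model, but to 100 imputed datasets. On observed data alone it drops patients without a Week 52 value (11% expected, about 4 of 36) and does not use their Week 26 data, which changes the missing-at-random handling of the primary analysis. Either combine it with the imputation in SAP 2.6.6 or state the loss.

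**Degrees of freedom.** Removing the between-within sentence is optional for two-visit endpoints and worth about 1 percentage point for four-visit ones.

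The cost is a few sentences of SAP text and changes to the TYPE= and DDFM= options. If a fallback is used and variance is in fact constant, intervals will be slightly wider.
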